### **1.5 Risks and Benefits**

There have been no serious adverse events related to the OptiScanner in any of the clinical studies performed to date.

Risk management in accordance with EN 14971, was completed on the study device. The conclusion is that the OptiScanner has an acceptable safety profile.

Because the OptiScanner system delivers automated, every 15 minutes glucose results and trends, it has the potential to improve a patient's glucose TIR by providing earlier identification of abnormal glucose values that would otherwise remain unknown until the clinical care scheduled glucose value was obtained (which typically are collected every 1 to 4 hours, depending on the condition of the patient). Therefore, the OptiScanner has the potential to improve all 3 domains of glycemic control: reducing hyperglycemia while at the same time preventing hypoglycemia and reducing glycemic variability. In the future, the OptiScanner may also reduce the workload associated with the high number of blood samples to be obtained and analyzed [22, 26-29].

## **2.0 Study Objectives**

The primary objective of this study is to observe the Time-in-Range for patients whose glycemic control is being monitored with the OptiScanner system. A secondary objective is assessment of the time it takes the patient to achieve in range glucose values while connected to the OptiScanner. The study will evaluate patients requiring frequent glucose monitoring in a Surgical ICU.

## **3.0 Selection and Withdrawal of Subjects**

### **3.1 Screening and Study Enrollment**

The study population includes surgical critical care patients who require blood glucose monitoring.

Subjects must have a vascular access device [i.e., Central Venous Catheters (CVC), Multi-lumen Access Catheters (MAC) either in place or to be placed with an expected usage of at least 48 hours.

Subjects that meet all of the eligibility criteria and are deemed suitable by the Investigator will be invited to participate in the study.

Each potential study subject, or their legally authorized representative, must provide written Informed Consent using the Institutional Review Board (IRB)/Ethics Committee (EC) approved Informed Consent Form before undergoing any study-related procedures.

A subject is considered enrolled in the study once the informed consent has been signed and all eligibility criteria have been verified, and the OptiScanner system has begun monitoring.

### **3.2 Inclusion Criteria**

All subjects are required to meet the following inclusion criteria in order to be considered eligible for participation in this study:

1. Signed informed consent by the participant or his/her legally authorized representative;
2. At least 18 years old;
3. Admitted to a Surgical ICU or planned admission to a Surgical ICU at time of screening
4. Expected SICU stay of at least 48 hours at the time of enrollment
5. A vascular access device available for connection to the OptiScanner is either already in-place, or is planned to be placed with an expected usage of at least 48 hours.

### **3.3 Exclusion Criteria**

Patients will be excluded from participating in this study if they meet any of the following exclusion criteria:

1. Positive HcG (serum or urine) in women of childbearing potential (age < 60) who are not known to be surgically sterile and those that are obviously pregnant.
2. Patients undergoing peritoneal dialysis within the past week.
3. Patients actively receiving intravenous immunoglobulin therapy.
4. Patients receiving intravenous administration of high dose ascorbate (IVC) for the treatment of patients with cancer.
5. Patients following the administration of a D-Xylose absorption test < 12 hours

6. Patients being treated with Sodium Thiosulfate.
7. Patients being receiving IV glycerol.
8. Patients receiving substances containing maltose, or substances that can be metabolized into maltose. These substances include Extranneal, Gamimune N, HepaGam B, Octagam, Vaccinia Immune Globulin, and WinRho SDF Liquid.
9. Hct <15% within 24 hours of screening visit.

### **3.4 Withdrawal of Subjects**

Subjects may voluntarily withdraw from the study at any time for any reason if they wish to do so, without any consequences. The PI may withdraw a subject from the study at his discretion due to safety or any other concerns (i.e. deliberate non-compliance).

## **4.0 Study Design**

### **4.1 Study Design Description**

This is a Single-center, non-randomized, study evaluating the TIR in a Surgical ICU population after implementing the OptiScanner system.

### **4.2 Insulin administration during the Study:**

#### **4.2.1 Phase One**

4.2.1.1 During Phase One of the trial, the hospital's current standard of care for glucose management will be followed. Currently glucose values are measured using point of care glucose meters and/or by collecting a blood sample and sending it to the hospital laboratory. Patients' glucose values are currently monitored depending on their clinical condition with the frequency of glucose measurement typically occurring every one to four hours. Patients enrolled in this study will still be monitored in this same manner, depending on their clinical condition (using point of care meters and/or blood collection for the lab). The additional continuous monitoring provided by the OptiScanner may introduce additional glucose measurements. The clinical care team will be advised to confirm any OptiScanner glucose value (using routine clinical care methods) before making any modifications to the patient's clinical care based on the OptiScanner result (i.e. increase, decrease, stop insulin drip, etc.). The glucose results from the OptiScanner will not be recorded in the medical record. A research team member will be at the bedside during the patients' connection to the OptiScanner to ensure that the clinical team does not use the OptiScanner results to direct patient care and to observe the overall clinical care glucose management of the patient. Representatives from the sponsor may be present at the participant's

bedside to provide the research team technical support and assistance. The sponsor representatives will not have access to the protected health information for the participant.

#### **4.2.2 Phase Two**

Following the 1st phase of the trial, data on time-in-range and patient glucose management activities and responsiveness to insulin adjustments will be assessed by the PI, a statistician, OptiScan and potentially, ICU nursing and physician leadership. Phase II Study procedures will be developed based on the results.

### **4.3 Study Endpoints and Other Assessments**

#### **4.3.1 Primary Endpoint**

The primary endpoint is an evaluation of the Glucose Time-in-range (TIR).

#### **4.3.2 Secondary Endpoint**

Assessment of the time it takes the patient to achieve in range glucose values while connected to the OptiScanner.

Target TIR		Primary Endpoint Evaluation of TIR
According to participants' clinical care defined target glucose range		

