**EXECUTIVE SUMMARY**

Sponsor Name:	This is an Investigator Initiated Study being funded by OptiScan Biomedical Corporation.
Objectives:	
Assessment of glucose Time-in-Range (TIR) post implementation of the OptiScanner 5000 bedside glucose monitoring system (OptiScan Biomedical) in a Surgical ICU patient population.
 
Assessment of the time it takes the patient to achieve in range glucose values (using participant's clinical care defined glucose target range) while connected to the OptiScanner.

Clinical Hypothesis:	
Preventing glucose variability has been shown to be strongly associated with increased survival in non-diabetic critically ill adults (6-8). In clinical practice, it is very challenging to maintain critically ill patients' glucose values within a "target range" as the methods currently available to accomplish this are burdensome on the clinical care team and can be quite costly.
 
The primary endpoint of this study is to assess the level of TIR obtained in a surgical ICU patient population after implementing the OptiScanner 5000 glucose monitoring systems.

Name of Investigational Device(s):	
OptiScanner 5000 Glucose Monitoring System
 
FDA Cleared on October 16, 2017 (K162042). The device will be used without Clinical Laboratory Improvement Amendments (CLIA) oversight for this study.

Design:	Single center, non-randomized, study evaluating the proportion of patients maintaining in range glucose values (using participants' clinical care defined glucose target range) and the time it takes for patients to achieve in range glucose values in a Surgical ICU population after implementing the OptiScanner 5000 Glucose Monitoring system

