#### **4.3.2 Additional Data Collected**

The following data will be collected during the OptiScanner evaluation:

- Demographic Data
- Date of admission
- Primary and secondary diagnosis
- History of thromboembolic events and clotting disorders
- Medications administered during ICU stay
- Insulin administration: timing, dosage, route and protocol used
- Insulin adjustment: reason for the adjustment, OS glucose value prior to insulin adjustment and standard of care confirmatory glucose value obtained if adjustment was related to an abnormal OS glucose value, timing of insulin adjustment, dosage, and route
- Dextrose administration/IV: timing, and dosage
- Dextrose adjustment: reason for the adjustment, OS glucose value prior to insulin adjustment and standard of care confirmatory glucose

value obtained if adjustment was related to an abnormal OS glucose value, timing of dextrose adjustment, dosage, and route

- TPN and other nutrition
- TPN and other nutrition adjustment
- Number of Hypoglycemic events (defined as glucose < 70 mg/dL)
- Number of Hyperglycemic events (defined as glucose > 200 mg/dL)
- Ventilator days, ICU LOS, and HLOS
- Infection outcome data
- Procedures including imaging, dialysis, and transfusions
- Date and time of OS connection/disconnect
- Contrast administration
- Discharge disposition (i.e. home, rehab, nursing home, death, etc.)
- Device related AE's and SAE's

Additional data not typically collected in the patient's medical records:

- Types and frequency of alarms (both dysglycemia and others) downloaded from the OptiScanner after the case
- The frequency of CVC maintenance incidents requiring disconnection from the OptiScanner system
- Comparator measurements (at the start, at approximately 24-hour intervals, and when prompted by the OptiScanner (i.e. cartridge change) Patients will have a study blood draw after OptiScanner connection, at approximately 24-hour intervals, and when prompted by the OptiScanner (i.e. cartridge change). The sample may be point of care or sent to the laboratory for analysis.
- History of CVC line (occlusions, other clotting disorders, age, etc)
- Clinical care team action/inaction details related to all glucose values (both OptiScanner and standard of care values).

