#### **4.5 Duration of Subject Participation**

Overall study enrollment is estimated to take approximately 12 months. Subjects enrolled in the study will participate for at least 48 hours and up to 72 hours. There are no follow-up visits or evaluation.

Participation in the study will be complete when either the subject is discharged from the SICU or hospital, or after 72 hours, whichever comes first.

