**7.0 Statistics**

For Phase One of this study, no formal statistics will be performed as this phase is strictly observational. Results of Phase One will be used to inform the power analysis for the 2nd phase of the study.

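### Does the secondary endpoint, time to reach in-range glucose, need to be restricted in the protocol to subjects out of range at connection?

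*Protocol*

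**What the plan says.** The endpoint in Section 4.3.2 (Secondary Endpoint) is "Assessment of the time it takes the patient to achieve in range glucose values while connected to the OptiScanner". Section 2.0 and the Executive Summary use nearly the same words. The Executive Summary adds that the range is the participant's own clinical-care target, and its Design row speaks of "the time it takes for patients to achieve in range glucose values in a Surgical ICU population". None of these places mentions glucose status at connection, and none names a time origin, a summary statistic or a rule for subjects who never reach range.

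Eligibility does not select on glucose level. Section 3.1 says "The study population includes surgical critical care patients who require blood glucose monitoring". The five inclusion criteria in Section 3.2 cover consent, age, surgical ICU admission, expected stay and vascular access, and none of the nine exclusions in Section 3.3 concerns the glucose value. Usual glucose management continues throughout Phase One (Section 4.2.1).

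On follow-up, Section 4.5 states "Participation in the study will be complete when either the subject is discharged from the SICU or hospital, or after 72 hours", whichever comes first. The Executive Summary counts a subject as evaluable after at least 48 hours of monitoring. The device reports about every 15 minutes (Section 1.5), all readings are stored and downloaded (Section 8.0), and the data list in Section 4.3.2 (Additional Data Collected) includes "Date and time of OS connection/disconnect".

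Section 7.0 plans no formal statistics for Phase One and adds "Results of Phase One will be used to inform the power analysis" for Phase Two.

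**The concern.** A subject whose first reading is already in range has nothing to achieve. That subject's time is either zero or undefined, and the protocol does not say which. Because usual care is running before and during monitoring, such subjects are likely to be enrolled.

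If they all entered as zeros, a mean or median time to range would depend on two things: the share in range at connection, and how quickly the others come into range. A cohort could look faster only because more of its patients started in control. Subjects who leave or reach 72 hours without an in-range value raise a second question, since dropping them would make control look quicker than it was. At stake would be the meaning of a descriptive summary and, if the number were carried forward, its use in planning Phase Two.

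**Working it through.** The protocol gives no figure for this endpoint and no derivation for its 50 subjects, so there is no stated number to reproduce. The check has two parts: how much pooling could matter, and whether the protocol calls for it.

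**Size under pooling (every input is an assumption)**

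Let *p* be the share in range at connection, with time 0, and let the rest have exponential times with mean 6 h. The median among subjects starting out of range is 6 ln 2 = 4.2 h.

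- Pooled median: solve *p* + (1 − *p*)F(t) = 0.5, which gives t = 6 ln[2(1 − *p*)] for *p* < 0.5, and 0 otherwise.
- Pooled mean: 6(1 − *p*).

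| *p* | Pooled median (h) | Pooled mean (h) |
|---|---|---|
| 10% | 6 ln 1.8 = 3.5 | 5.4 |
| 20% | 6 ln 1.6 = 2.8 | 4.8 |
| 30% | 6 ln 1.4 = 2.0 | 4.2 |
| 40% | 6 ln 1.2 = 1.1 | 3.6 |
| 50% | 0 | 3.0 |

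A lognormal with the same median and sigma 1 is more skewed: its skewness is (e + 2)√(e − 1) = 6.2, against 2 for the exponential. It gives pooled medians of 3.6, 3.0, 2.4 and 1.6 h at 10% to 40%, so the pattern does not depend on the exponential shape.

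With 50 subjects the sample median is exactly zero when 26 or more start in range. P(Binomial(50, *p*) ≥ 26) is 0.001, 0.06, 0.44 and 0.90 at *p* = 30%, 40%, 50% and 60%.

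**Subjects who never reach range**

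If a share *c* of those starting out of range never reach it, keeping them as censored means solving (1 − *c*)F(t) = 0.5. This gives 4.9 h at *c* = 10% and 5.9 h at *c* = 20%, against 4.2 h if they are dropped. These shares do not fit the same 6 h model, under which P(T > 48 h) = exp(−8) = 0.03%. An evaluable subject also has at least 48 hours of monitoring, or 48 × 4 = 192 readings at 15-minute spacing. To have no value, such a subject would need to show no in-range reading in all that time.

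**What the protocol actually calls for**

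1. The pooled result needs four choices: all enrolled subjects, a clock starting at connection, zeros for those already in range, and a single mean or median. The protocol makes none of them.
2. Time taken to achieve a state ordinarily presupposes not yet being in it. The restricted reading is at least as natural as the pooled one.
3. Sections 4.2.2 and 4.4.2 list what will be assessed before Phase Two: time-in-range, glucose management activities and responsiveness to insulin adjustments. Time to reach range is not named.
4. The Executive Summary says the protocol will be updated with Phase Two procedures after Phase One is analysed. Any definition needed for a comparison can be set then.
5. Stored readings and recorded connection times allow the restricted summary, the count already in range, and censoring at disconnection to be produced later without new data.

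**The case for a change.** The best case for a change is that the population an endpoint applies to belongs in the protocol, which words this one several times for the patient without limit. An SAP that restricted it would be narrowing a stated endpoint. The mixing can even reverse a comparison. Under exponential times with median *m*, the pooled median is *m* log₂[2(1 − *p*)]. A cohort with *m* = 8 h and 40% in range at connection gives 8 × log₂ 1.2 = 2.1 h, which looks faster than one with *m* = 4 h and 20% in range, at 4 × log₂ 1.6 = 2.7 h. Clarifying would take only a sentence.

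The arithmetic stands, and so does the observation that the text is silent. What does not stand is the step from silence to error. The protocol permits the poor summary but does not ask for it, and it plans no between-phase or between-group comparison on this endpoint for case mix to distort. Restriction also has a cost: at in-range shares of 10%, 30% and 50%, the contributors fall to 50 × 0.9 = 45, 50 × 0.7 = 35 and 50 × 0.5 = 25. It also conditions on a single first reading, which invites regression to the mean. Showing the share at time zero beside the distribution for the rest would serve the reader equally well.

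A neighbouring wording mismatch adds nothing here. Section 2.0 says "The study will evaluate patients requiring frequent glucose monitoring in a Surgical ICU", and Section 3.1 likewise refers to a need for monitoring, while the list in Section 3.2 carries no such criterion. Needing monitoring is not the same as being out of range, so aligning those sections would leave the endpoint question where it is.

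**Conclusion.** No change to the plan is needed. The gap is real but ordinary: who contributes a time, where the clock starts and how non-achievers are treated are analysis details for a descriptive secondary endpoint. The SAP, which was not available here, commonly settles them. An analyst facing zeros at connection would report how many subjects were already in range and describe the time for the others, and the stored data support this fully.

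If pooling were nevertheless done, the effect could be large. Under the assumed 6 h exponential, the median falls from 4.2 h with nobody in range at connection to 2.0 h at a 30% share and to zero at 50%. The in-range share, the time distribution and the never-reach share are all assumptions, so the document cannot say where in that span the trial would fall. No error rate or formal test depends on the answer. The link to Phase Two is only the general statement in Section 7.0 that Phase One results inform its power analysis.

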#### **4.3.2 Additional Data Collected**

The following data will be collected during the OptiScanner evaluation:

- Demographic Data
- Date of admission
- Primary and secondary diagnosis
- History of thromboembolic events and clotting disorders
- Medications administered during ICU stay
- Insulin administration: timing, dosage, route and protocol used
- Insulin adjustment: reason for the adjustment, OS glucose value prior to insulin adjustment and standard of care confirmatory glucose value obtained if adjustment was related to an abnormal OS glucose value, timing of insulin adjustment, dosage, and route
- Dextrose administration/IV: timing, and dosage
- Dextrose adjustment: reason for the adjustment, OS glucose value prior to insulin adjustment and standard of care confirmatory glucose

value obtained if adjustment was related to an abnormal OS glucose value, timing of dextrose adjustment, dosage, and route

- TPN and other nutrition
- TPN and other nutrition adjustment
- Number of Hypoglycemic events (defined as glucose < 70 mg/dL)
- Number of Hyperglycemic events (defined as glucose > 200 mg/dL)
- Ventilator days, ICU LOS, and HLOS
- Infection outcome data
- Procedures including imaging, dialysis, and transfusions
- Date and time of OS connection/disconnect
- Contrast administration
- Discharge disposition (i.e. home, rehab, nursing home, death, etc.)
- Device related AE's and SAE's

Additional data not typically collected in the patient's medical records:

- Types and frequency of alarms (both dysglycemia and others) downloaded from the OptiScanner after the case
- The frequency of CVC maintenance incidents requiring disconnection from the OptiScanner system
- Comparator measurements (at the start, at approximately 24-hour intervals, and when prompted by the OptiScanner (i.e. cartridge change) Patients will have a study blood draw after OptiScanner connection, at approximately 24-hour intervals, and when prompted by the OptiScanner (i.e. cartridge change). The sample may be point of care or sent to the laboratory for analysis.
- History of CVC line (occlusions, other clotting disorders, age, etc)
- Clinical care team action/inaction details related to all glucose values (both OptiScanner and standard of care values).

#### 4.3.3 Safety Endpoint

The proportion of subjects that experience one or more Device Related Serious Adverse Events (DRSAEs). Incidence of hypo/hyperglycemia.

#### 4.4 **Sample Size**

A minimum of 50 subjects will be enrolled in the study. The study will be divided into 2 phases: Phase One and Phase Two.

##### 4.4.1 Phase One:

Phase One of the study will consist of study staff working with the clinical care team to operationalize the logistics involved with implementing the OptiScanner. In addition, phase one subjects will provide the opportunity for the PI to observe the OptiScanner

utility as a complement to the current glucose management of the patient. The continuous glucose monitoring provided by the OptiScanner may introduce additional glucose measurement information that would not have been known if it occurred between the routine clinical care glucose measurements and the clinical care team will be advised to confirm any OptiScanner glucose value (using routine clinical care methods) before making any modifications to patients' clinical care based on the OptiScanner glucose result. A research team member will be at the patient's bedside during his/her entire study participation to ensure that the clinical care team does not use the OptiScanner results independently to direct patient care and to observe how the additional glucose information is or is not used. A minimum of 50 patients will be enrolled in phase one.

#### **4.4.2 Phase Two:**

Following the 1st phase of the trial, data on time-in-range and patient glucose management activities and responsiveness to insulin adjustments will be assessed by the PI, a statistician, OptiScan and potentially, ICU nursing and physician leadership. Phase II Study procedures will be developed based on the results.

#### **4.5 Duration of Subject Participation**

Overall study enrollment is estimated to take approximately 12 months. Subjects enrolled in the study will participate for at least 48 hours and up to 72 hours. There are no follow-up visits or evaluation.

Participation in the study will be complete when either the subject is discharged from the SICU or hospital, or after 72 hours, whichever comes first.

